2 STUDY OBJECTIVES

2.1 Primary Objective

The primary objective is:

- To examine the efficacy of piano training to improve CAP, cognition, and everyday function among older adults across baseline to immediate post-test. We will assess the effects of piano training (intervention) as compared to music listening instruction (active control) on CAP, cognition, and everyday function. The primary outcome of interest is cognition.

Hypotheses: The piano training group will outperform the music listening instruction group on measures of CAP, cognition, and everyday function immediately post-intervention.

Rationale: The efficacy of a novel intervention will be established relative to an active control group. There is compelling evidence that CAP deficits contribute to cognitive difficulties²⁻⁵ and are a risk factor for dementia^{3,6,7}. We propose that enhancing CAP may be particularly important to improve cognitive function. Formal music training is longitudinally associated with enhanced CAP and successful cognitive aging. Piano training is a feasible, potentially efficacious intervention to improve older adults' CAP and cognition.

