9.6 Final Data Analyses

Dealing with Score Distribution. We will inspect the distribution of scores to confirm that parametric statistical testing is appropriate. In the event that distributional properties do not support parametric tests, we will compare the results from conventional parametric analyses with (a) results from similar nonparametric testing (e.g., Wilcoxon signed ranks test), (b) results from parametric analyses conducted after the non-normally distributed variables are transformed to improve normality to compare the results with the conventional parametric analyses, and (c) Any illegal values or outliers of $\geq \pm 3z$ will be checked for accuracy with the raw data.

Composite Outcomes. Data reduction in the form of principal component factor analysis (PCA) will be used to derive composite outcomes of CAP, cognition, and everyday function for analyses to reduce the number of comparisons. Baseline data across CAP, cognitive, and everyday function outcomes will be factor analyzed using pairwise deletions. Based on the number of factors derived and factor loadings of the individual measures (.4 or greater), outcome composite scores will be calculated after transforming the baseline data to z scores while taking into account the directional scaling of the items. Post-test scores will be standardized based upon the baseline mean and SD. The baseline factors and loadings will be applied to calculate post-test composite scores.

Preliminary/Descriptive Analyses. Prior to the analyses described below, we will conduct one-way ANOVA or Chi-square analyses as appropriate comparing the randomized groups at baseline on age, race, education, sex, MoCA, GDS, hearing and vision, to ensure that the study randomization procedures were successful. We will also confirm the equivalence of the two randomized conditions by comparing the NICT questionnaire responses. The total across the six items relevant to cognition will be calculated and examined in analyses. If even a marginally significant ($p < .1$) difference is observed for any of these study variables, the pertinent variables will be included as covariates in subsequent analyses.

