The randomized groups did not differ in sex, $\chi^2(1)=.787, p=.375$, ethnicity $\chi^2(1)=.167, p=.683$, or race, $\chi^2(1)=.045, p=.832$. The Music Reading Assessment scores did not differ between the two groups, $t(266)=-.958, p=.338$. The randomized groups did not significantly differ in age, $F(1,266)=.293, p=.589$, education, $F(1,266)=.369, p=.544$, MoCA, $F(1,266)=.427, p=.514$, or GDS, $F(1,266)=.943, p=.332$. However, there were marginally significant group differences for PTA in the left ear, $F(1,266)=3.31, p=.070$ and statistically significant group differences for both PTA in the right ear, $F(1,266)=6.69, p=.010$, and visual acuity, $F(1,266)=8.99, p=.003$. The music listening group tended to have worse hearing, while the piano training group tended to have worse visual acuity. See Table 1. The groups also differed significantly in their expectations regarding potential benefits of their randomized group, $F(1,214)=15.07, p<.001$. The piano training group had an average rating of 5.55 while the music listening group had an average rating of 4.99, indicating the piano training condition had higher expectations about the potential effects of their randomized condition. The piano training group also rated their condition as more challenging with 92% agreeing that the intervention was challenging as compared to 86.3% of the music listening group indicating their condition was challenging ($p<.001$).

Principal component analysis with varimax rotation was conducted to reduce the number of variables for analyses. Please see Supplemental Table A for details. The first factor reflected cognitive performance speed and included the Trail Making Test, Digit Coding, and the TEA visual elevator and phone search subtests. The second factor included all three verbal fluency subtests. The third factor reflected CAP and included DDT, DSI, TCS, and WIN. The fourth factor included two indices from the TEA phone search while counting and visual elevator accuracy. The fifth composite included ATTR across- and within- channel performance. Baseline composites of cognitive performance, verbal fluency, ATTR, CAP, and everyday function were created by averaging z scores after the reverse-scaling of items with negative factor loadings. Post-test scores were standardized

by baseline means and *SDs*. Timed IADL performance did not significantly load on any factor and was thus examined separately.

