Hearing	-0.09	0.06	.134	-0.14	0.06	.016
Visual acuity	-6.55	5.33	.220	-15.45	5.12	.003
Expectations	-0.79	0.67	.234	-1.96	0.64	.003
	Timed IADL+			Test of Everyday Attention		
Intercept	48.89	1.32	<.001	62.34	1.15	<.001

Group	3.15	2.67	.240	1.37	2.33	.557
Time	0.14	0.79	.863	-8.61	0.67	<.001
Group x time	-1.53	1.58	.327	-0.40	1.340	.765
Hearing	0.07	0.57	.194	-0.02	0.05	.603
Visual acuity	12.75	4.770	.008	0.24	4.470	.957
Expectations	1.02	0.59	.089	-0.79	0.56	.157

Note. ATTR=Adaptive Tests of Temporal Resolution, IADL=instrumental activities of daily living. MCI=mild cognitive impairment. +For ATTR and Timed IADL lower scores reflect better performance.

Table 14.3. *Effect sizes for piano training relative to music listening across composite outcomes and assessments for the analytic sample overall, among those adherent, and by cognitive status.*

Outcome Measure	d Effect Size			
	Overall (n =198)	Adherent (n =189)	Non-MCI (n =146)	MCI (n =52)
Central auditory processing composite	-0.01	-0.01	0.00	-0.07
Dichotic Digits	-0.06	-0.07	-0.03	-0.14
Dichotic Sentence Identification	0.01	0.01	0.02	-0.07
Time Compressed Speech	-0.01	0.01	0.03	-0.06
Words in noise	0.03	0.03	0.12	0.01
Adaptive Tests of Temporal Resolution composite	0.17	0.20	-0.09	0.24
Cognitive composite	-0.03	-0.03	-0.10	0.08
Trails A	0.03	0.06	0.00	0.43
Trails B	-0.17	-0.20	0.01	-0.54
Digit Symbol Coding	0.08	0.09	0.06	0.26
Test of Everyday Attention - Visual elevator timing subtest	0.02	0.02	0.03	0.44
Test of Everyday Attention - Telephone search time	-0.29	-0.32	0.08	-0.27
Verbal fluency composite	0.05	0.06	0.09	-0.12

Letter fluency	0.00	0.02	0.09	-0.36
Category fluency	0.18	0.20	0.18	0.13
Switching fluency	-0.06	-0.05	-0.07	-0.05
Test of Everyday Attention composite	0.04	0.08	-0.30	-0.02
Visual Elevator accuracy	0.01	0.03	-0.12	-0.19
Dual task decrement	0.10	0.13	-0.18	0.22
Timed Instrumental Activities of Daily Living composite	-0.15	-0.21	0.09	-0.13

Note. MCI=mild cognitive impairment. *d* effect sizes were calculated as pre- to post- change in the piano training condition relative to the music listening condition divided by the baseline standard deviation such that positive values would indicate improvement. Adherent analyses include those who completed 15 or more sessions of the assigned condition.

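### Table 14.3: the cognition composite without MCI (-0.10) conflicts in sign with the five tests it averages (0.00 to 0.08), so some printed effect sizes for the primary outcome must be wrong

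*Combined protocol and SAP*

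**What the plan says.** Section 2.1 states: "The primary outcome of interest is cognition". Section 9.6 (Composite Outcomes) plans that "outcome composite scores will be calculated after transforming the baseline data to z scores while taking into account the directional scaling of the items", and adds: "The baseline factors and loadings will be applied to calculate post-test composite scores".

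Section 14 reports what was done. On membership: "The first factor reflected cognitive performance speed and included the Trail Making Test, Digit Coding, and the TEA visual elevator and phone search subtests". On scoring, the composites "were created by averaging z scores after the reverse-scaling of items with negative factor loadings", with post-test scores standardised on baseline means and SDs. The three verbal fluency tests formed a separate factor.

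The note to Table 14.3 says that "effect sizes were calculated as pre- to post- change in the piano training condition relative to the music listening condition divided by the baseline" SD, "such that positive values would indicate improvement". The table prints one n per column: 198 overall, 189 adherent, 146 without MCI and 52 with MCI. It gives no n per row and no other weighting rule.

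**The concern.** An average of direction-aligned z scores is linear in its members. A difference in change on the composite is therefore the average of the differences on the members, rescaled by one positive number. If no member is negative, the composite cannot be clearly negative. In the column without MCI it is.

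What is at stake is the effect size for the larger of the two named primary-outcome composites' subgroups. A reader cannot tell whether the cognition effect without MCI was about +0.05 or -0.10. As printed, the composite contrast between MCI and no MCI is 0.08 - (-0.10) = 0.18. From the member rows it is (0.064 - 0.036) divided by the composite SD, or about 0.03 to 0.04 for r from 0.7 to 0.3. Section 14 draws its statements about who did and did not improve from this table.

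**Working it through.** **Inputs.** All effect sizes come from Table 14.3. The average inter-test correlation r is not given, so it is an assumption, ranged from 0 to 1.

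**Formula.** For K baseline-standardised, aligned z scores with equal weights, d(composite) = mean(d of members) / S, where S = sqrt((1 + (K - 1)r) / K). S is at most 1, so the composite has the sign of the member mean and is at least as large.

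**Check of the method on verbal fluency (K = 3).** Member means are 0.040, 0.057, 0.067 and -0.093 (overall, adherent, without MCI, MCI). Printed composites are 0.05, 0.06, 0.09 and -0.12. The implied S is 0.80, 0.94, 0.74 and 0.78, all admissible. The rule reproduces the table in all four columns.

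**Cognition (K = 5).**

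| | Overall | Adherent | No MCI | MCI |
|---|---|---|---|---|
| Trails A | 0.03 | 0.06 | 0.00 | 0.43 |
| Trails B | -0.17 | -0.20 | 0.01 | -0.54 |
| Digit Symbol Coding | 0.08 | 0.09 | 0.06 | 0.26 |
| Visual elevator timing | 0.02 | 0.02 | 0.03 | 0.44 |
| Telephone search time | -0.29 | -0.32 | 0.08 | -0.27 |
| Member mean | -0.066 | -0.070 | +0.036 | +0.064 |
| Implied composite, r = 1 to 0 | -0.07 to -0.15 | -0.07 to -0.16 | +0.04 to +0.08 | +0.06 to +0.14 |
| Printed composite | -0.03 | -0.03 | -0.10 | 0.08 |

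**Without MCI.** At r = 0.3, S = sqrt(2.2/5) = 0.663 and the composite is 0.036/0.663 = +0.054. At r = 0.5, S = 0.775 and it is +0.046. Taking every entry 0.005 lower leaves a mean of +0.031. Loading weights or subgroup SDs only replace equal weights by other positive weights, and the one member that could be below zero before rounding is Trails A, at no less than -0.005. Neither can give -0.10. A composite of -0.10 needs a member mean of -0.10 x 0.663 = -0.066 (r = 0.3) to -0.10 x 0.775 = -0.077 (r = 0.5), a gap of 0.10 to 0.11 z from +0.036.

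**Scoring direction.** Of the 32 sign patterns for the five tests, with a common r of 0.2 to 0.8, none comes within 0.08 of all four printed values. One pattern reaches -0.10 without MCI (r about 0.6), but it then gives about -0.34 for MCI, against +0.08 printed.

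**Overall and adherent.** These mismatches are of size only and rest on equal weights. With weights of 0.4 on Trails B and telephone search (the loading threshold in 9.6) and 1 on the rest, the overall weighted mean is (0.03 - 0.068 + 0.08 + 0.02 - 0.116)/3.8 = -0.014. Unequal weights could therefore reach -0.03, though Section 14 describes plain averaging.

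**Which rows look wrong.** Assume equal SDs and the same arm split in both subgroups. Then d without MCI = (198 x overall - 52 x MCI)/146:
- Trails A: (5.94 - 22.36)/146 = -0.112
- Trails B: (-33.66 + 28.08)/146 = -0.038
- Digit Symbol Coding: (15.84 - 13.52)/146 = +0.016
- Visual elevator timing: (3.96 - 22.88)/146 = -0.130
- Telephone search: (-57.42 + 14.04)/146 = -0.297

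The mean is -0.112, against +0.036 from the printed rows. It has the direction of the printed composite, although dividing by S gives about -0.15 to -0.17 at r = 0.5 to 0.3, so the match in size is rough. The composite row itself reconciles better: (146 x -0.10 + 52 x 0.08)/198 = -0.05, against -0.03 printed. Telephone search reconciles worst: (146 x 0.08 + 52 x -0.27)/198 = -0.01, against -0.29 printed. Even with the MCI SD at its limit of sqrt(198/52) = 1.95 times the overall SD, and no offset from the other subgroup, it reaches only -52 x 0.27 x 1.95/198 = -0.14.

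**CAP.** Its four members average -0.0075, -0.005, +0.035 and -0.065, against -0.01, -0.01, 0.00 and -0.07 printed. Only the column without MCI fails.

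**The case against.** A reader might infer that the primary group x time test in Table 14.2 was run on a variable other than the one described. The documents do not support that. If music listening is the higher-coded arm and scores are T-scaled with SD 10 (both assumptions), the Table 14.2 estimates convert to d as follows, with Table 14.3 in brackets: ATTR 0.15 (0.17), CAP -0.05 (-0.01), verbal fluency 0.03 (0.05), cognition -0.04 (-0.03), Timed IADL -0.15 (-0.15) and TEA 0.04 (0.04). All six agree in sign. This does not prove item membership, but it suggests that the composite row and the model describe the same score.

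A reader might also infer that the composite's sign without MCI is the error. That is so only if the member rows are right, and those reconcile worse with the other columns.

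The TEA composite without MCI (-0.30, over printed members of -0.12 and -0.18) is tempting as a further example. Section 14 can be read as giving that factor three members, of which two are printed, so nothing follows.

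Different participants per row could in principle explain the conflict, since no n per row is given. But the gap of 0.10 to 0.11 z is large for 146 people, and one n is printed per column. Supplemental Table A, which holds the loadings, is not in the documents, but positive weights cannot remove the sign conflict.

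The objection on importance stands. Section 14 reports group x time p values above .194 and three-way MCI p values above .245. Aim 2 rests on that interaction, not on Table 14.3. The PCA also split planned cognition into this composite and verbal fluency.

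**Conclusion.** The contradiction is real in the column without MCI: -0.10 is printed where the stated rule gives about +0.04 to +0.08 (+0.03 to +0.09 with rounding). The sign conflict needs no assumption about correlation or exact weights, only aligned scoring, positive weights and the same participants in each row of a column. The overall and adherent composites are too small by about 0.04 even at r = 1, but that rests on equal weights. The MCI column agrees.

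The documents do not settle which rows are wrong; the single-test rows without MCI are at least as suspect as the composite, given equal SDs and arm splits. Table 14.2 is not shown to be wrong. This should be fixed because effect sizes printed for the named primary outcome cannot all be right, but no significance conclusion is shown to change.

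**What to change.** Recompute every row of Table 14.3, single tests as well as composites, from the existing data, using the same participants for a composite and its members within each column. Confirm item membership, direction of scoring, weights, and whether whole-sample or subgroup SDs were used. Print n per row and correct whichever rows are wrong, together with any sentence in Section 14 that relies on them. Reprinting only the composite rows could leave the error in place.

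If the check shows that the cognition score was not built as Section 14 describes, either correct that description or rebuild the score and rerun the cognition model and its MCI interaction. Otherwise no model needs rerunning. The cost is rerunning existing scoring code; no new data are needed.

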2.2 Secondary Objectives

The secondary objectives are:

- To examine the moderating effects of MCI on piano training efficacy. Moderating effects of MCI status will determine if piano training is effective for older adults with and/or without MCI.

Rationale: It is possible that piano training is effective prior to cognitive decline, but not in those with MCI. It is also possible that cognitive and/or functional abilities may be differentially enhanced among those with and without MCI. Delineating the effects of piano training among those with and without MCI will discern who is most likely to benefit from piano training, and for what specific outcomes. We do not have a directional hypothesis for this objective.

- To explore mediators of intervention effects.

Hypothesis: Grounded in theory⁸ and prior research⁹⁻¹¹, we hypothesize that piano training will improve CAP and cognitive performance, leading to functional improvements. We expect that enhanced CAP will mediate cognitive gains. We further hypothesize that cognitive gains will mediate functional improvements.

Rationale: Crucially, we must discern the underlying mechanisms of effective interventions in order to maximize training gains.

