9.3 Sample Size

We expect up to 20% attrition after the initial in-person visit across the time period in which cognitive intervention study protocols will be administered. Our goal is to complete in-person screening visits for up to 450 participants in order to have up to 360 participants complete the study. We can tolerate higher rates of attrition. We require a minimum of 198 eligible participants with *at least* 99 individuals randomized to each condition (piano training, controls) to have adequate statistical power. With stratified randomization, this will result in *at least* 48 persons per MCI/no MCI subgroup.

Statistical power analysis using G*Power¹²³ in consideration of our pilot data effect sizes as well as attrition was conducted to estimate power. We will control type I error at .05 to achieve at least 80% statistical power.

To power **Specific Aim 1: To examine the efficacy of piano training to improve CAP, cognition, and everyday function among older adults**, a final n of 198 participants ($n=99$ per randomized condition) will achieve 95% power to detect a significant group x time interaction across baseline to immediate post-test, with an alpha of .05. This assumes a small effect size (f) of 0.10¹²⁴ (Cohen's f effect sizes are 0.10- small, 0.25- medium: f is roughly equivalent to $\frac{1}{2}$ of d when comparing two groups)¹²⁴.

To power **Specific Aim 2: To examine the moderating effects of MCI on intervention efficacy**, a final n of 168 will have .95 power at alpha .05 to detect medium effects ($f=.10$) for significant group x time x moderator three way interactions.

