9.5 Interim Data Analyses

Interim analyses will be conducted in June of 2019, after the pilot, first, and second replicates are completed. We expect that 140 participants will have completed post-test at this time. The purpose will be to confirm feasibility of the training conditions, to assess effect size on cognitive measures from pre- to post- training and adapt number of sessions, if warranted, and to monitor safety.

Interim analyses will be conducted to ensure the safety of the trial. Per NIA, this project does not meet the criteria for requiring a formal Data and Safety Monitoring Plan or Data Safety Monitoring Board because it is not a Phase III clinical trial as defined by NIH. As a behavioral intervention study, this is a phase II efficacy trial¹. At interim analysis, [name] will compare the number of adverse events between the two randomized conditions to assess safety. The two groups will also be compared on attrition rates. Any significant differences between the two conditions in adverse events or attrition rates will be further investigated by [name]. If there is a significant imbalance, confirmed, then [name] will report the findings to the Clinical Trial Coordinator, [name], who is unblinded. The Clinical Trial Coordinator will work with the IRB to decide if the study should be terminated early.

Interim analyses will be conducted to ensure the feasibility of study intervention adherence. If at interim analyses, less than 75% of participants randomized to an arm complete at least 16 sessions (80% of prescribed 20), the intervention arm will be deemed not feasible. If this occurred for both arms, the study will end.

Finally, interim analyses will examine the potential efficacy of the piano training arm. Effect sizes and confidence intervals for all cognitive outcomes will be calculated for pre- to post- training relative to controls. We expect that the piano training arm will produce an improvement of at least $d=0.25$ from baseline to post-test on at least one of the cognitive measures of verbal fluency (phonemic, category or switching), Trails A or B, or Digit Coding, relative to active controls. If an effect size from pre- to post- training relative to controls of this

magnitude is not observed on at least one of these outcomes, we will adapt study procedures by changing the number of training sessions from 20 to 25. In this instance number of training sessions completed will be examined as a covariate in final analyses.

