Specific Aim 2: To examine the moderating effects of MCI on intervention efficacy. We will also test for moderation effects to determine at what stage along the cognitive status continuum—without MCI vs. MCI—intervention is most effective. To do so, we will examine three-way interactions (MCI x training group x time) for the CAP, cognitive, and everyday function composites. When an interaction is significant, we will stratify analyses by MCI status and examine effect sizes. Effect sizes from pre- to post- training relative to controls will be compared for participants with/without MCI. An alpha of .05 will be used for these analyses.

Participants who score 26 or higher on the MoCA will be defined as no MCI (i.e., cognitively normal). Those participants who score a 20-25 on the MoCA will be defined as MCI if they score a 0.5 on the CDR and have performance at or 1 SD below their age, sex, and education norms on any of the following measures: Trails, Verbal Fluency, Digit Coding, Craft Story Recall, Multilingual Naming Test, or Benson Complex Figure. Those with MoCA scores 20-25 who score 0 on the CDR, but have performance at or 1SD below expected for age, sex, and education will be adjudicated prior to analyses. If an individual scores 20-25 on the MoCA, and 0.5 on the CDR, but has performance above expected on all of the aforementioned measures, their case will be adjudicated prior to analyses. The study physicians will adjudicate such cases prior to coding of MCI status for final analyses.

To quantify the effects of piano training further, in addition to examining composite outcomes as detailed above, we will calculate and report effect sizes for pre-to-post change of piano training relative to controls for each individual measure of CAP, cognition, and everyday function for the sample overall as well as stratified by MCI status and among those who were adherent only (80% or more of sessions completed).

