In the primary analyses, we examined whether performance changed differentially by random assignment across composite outcomes from baseline to post-test as indicated by a significant group-by-time interaction. Covariates included hearing PTA, visual acuity, and expectations. The group-by-time interactions were not statistically significant for any of the outcomes ($ps > .194$). See Table 2. The results did not change when we included only those who were adherent ($ps > .180$). See Supplementary Table B. Piano training did not significantly enhance CAP, cognition, or everyday function as compared to music listening. We further examined if intervention effects varied by MCI status (Supplementary Table B). There were no significant group-by-time-by-MCI status interactions indicating those with and without MCI did not show differential benefit ($ps > .245$). Thus, MCI did not significantly moderate the effects of piano training.

Effect sizes for piano training as compared to music listening are shown in Table 3. Improvements were not evident in the primary analyses, adherent analyses, or the subsample without MCI on measures of CAP, cognition, or everyday function. Participants with MCI randomized to piano training showed potential small effect sizes for improvement relative to music listening on Trails A, Digit Symbol Coding, and one subtest of the TEA ($ds \geq 0.25$). Raincloud plots of individual assessment and composite variables are included in the supplemental materials.

Results indicated significant effects of time for ATTR in all models and significant effects of time for CAP in the primary and adherent analyses indicating improved performance from pre- to post- training. Significant effects of time were found for cognition and TEA in the primary and adherent analyses, indicating a tendency for decline across time. With respect to covariate effects, CAP, ATTR, and cognitive performance were significantly impacted by hearing. Similarly, Timed IADL and cognitive performance varied significantly by visual acuity. Those with poorer hearing or vision tended to perform worse on these outcomes. Interestingly,

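### Section 14 reads non-significant MCI interactions as evidence of no differential benefit, although differences of about 0.3 to 0.7 SD cannot be excluded

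*Combined protocol and SAP*

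**What the plan says.** Section 2.2 makes moderation by MCI status a secondary objective, meant to show who is likely to benefit, and adds: "We do not have a directional hypothesis for this objective". Section 9.6 (Specific Aim 2) tests it by the MCI x group x time interaction on each composite: "An alpha of .05 will be used for these analyses". No equivalence margin is set.

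On effect sizes, Section 9.6 states that "we will calculate and report effect sizes for pre-to-post change of piano training relative to controls", for each measure, overall and by MCI status. It does not ask for intervals. Section 9.5 does, for the interim look: "Effect sizes and confidence intervals for all cognitive outcomes will be calculated".

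Section 14 then reports: "There were no significant group-by-time-by-MCI status interactions indicating those with and without MCI did not show differential benefit", all p-values being above .245. The next sentence says only that MCI was not a significant moderator. The next paragraph mentions possible small effects (d of 0.25 or more) in the MCI group on Trails A, Digit Symbol Coding and one TEA subtest. Table 14.3 gives d for 146 participants without MCI and 52 with MCI, with no intervals. The three-way results are referred to Supplementary Table B, which is not among the documents.

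**The concern.** A p-value above .05 for an interaction supports a claim of no difference only if the interval around the estimate is narrow enough to rule out differences that would matter. The quoted clause makes the claim without an interval and without a margin. The smaller stratum has 52 people, so the interaction is estimated much less precisely than the main effect.

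What is at stake is the answer to Aim 2. A reader could conclude that the response to piano training has been shown to be alike with and without MCI. The same section then points to possible MCI-only effects, and the main text and tables give no interval with which to judge either statement.

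**Working it through.** **Planned power for Aim 2.** Section 9.3 gives power .95 at n = 168, f = .10, alpha .05. The usual repeated-measures formula is a noncentral F with lambda = N x f² x 2 / (1 - rho). The pre-post correlation rho is not stated. The Aim 1 figure (n = 198, f = .10, power .95) is reproduced at rho = .70 (.951). At that rho, Aim 2 gives .914 with 1 numerator df or .801 with 3. It reaches .95 only at rho of about .74 to .75 (1 df), or a little above .80 (3 df). So the Aim 2 figure depends on an unstated correlation different from the one Aim 1 implies. Nothing below uses it.

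**Inputs.** Group x time standard errors from Table 14.2; n = 52 and 146 (total 198) from Table 14.3.

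**Formula.** With equal arms and a common SD of change s, the overall group x time SE is 2s/√198 and each stratum SE is 2s/√n. Hence

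SE(three-way) = SE(group x time) x √[198 x (1/52 + 1/146)] = SE(group x time) x 2.272.

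Dividing by 10 gives baseline SD units if the composites have SD 10. The half-width is 1.96 x SE, and the difference detectable with 80% power is 2.80 x SE. Power for a true difference of 0.25 is Φ(0.25/SE - 1.96) + Φ(-0.25/SE - 1.96).

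| Composite | SE, Table 14.2 | SE three-way (SD) | 95% half-width | Detectable, 80% power | Power for 0.25 |
|---|---|---|---|---|---|
| CAP | 0.71 | 0.161 | 0.32 | 0.45 | 34% |
| Cognition | 0.84 | 0.191 | 0.37 | 0.53 | 26% |
| Verbal fluency | 0.96 | 0.218 | 0.43 | 0.61 | 21% |
| TEA | 1.34 | 0.305 | 0.60 | 0.85 | 13% |
| ATTR | 1.35 | 0.307 | 0.60 | 0.86 | 13% |
| Timed IADL | 1.58 | 0.359 | 0.70 | 1.01 | 11% |

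An interval whose half-width exceeds 0.25 contains a value beyond +0.25 or -0.25 wherever it is centred. All six do.

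**Intervals using the d values as printed (MCI minus non-MCI, Table 14.3).**
- Cognition: 0.08 - (-0.10) = 0.18 (-0.19 to 0.55)
- Verbal fluency: -0.12 - 0.09 = -0.21 (-0.64 to 0.22)
- CAP: -0.07 - 0.00 = -0.07 (-0.39 to 0.25)
- ATTR: 0.24 - (-0.09) = 0.33 (-0.27 to 0.93)
- TEA: -0.02 - (-0.30) = 0.28 (-0.32 to 0.88)
- Timed IADL: -0.13 - 0.09 = -0.22 (-0.92 to 0.48)

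The centres need a warning. The non-MCI cognitive composite is printed as -0.10, but the five components that Section 14 assigns to it are 0.00, 0.01, 0.06, 0.03 and 0.08, none of them negative. For Timed IADL the overall value (-0.15) lies outside the two subgroup values (0.09 and -0.13). The same is true of the TEA composite (0.04 against -0.30 and -0.02). The half-widths do not depend on these values.

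**Checks on the assumptions.**
- Scale: the Table 14.2 group x time estimates divided by 10 are, in absolute value, 0.15 (ATTR), 0.05 (CAP), 0.03 (verbal fluency), 0.04 (cognition), 0.15 (Timed IADL) and 0.04 (TEA). The overall d values in Table 14.3 are 0.17, 0.01, 0.05, 0.03, 0.15 and 0.04 in absolute value. That fits SD 10.
- p-values: the derived SEs and printed differences imply p from .28 to .66, in line with the reported bound of .245.
- Sample: an assumed split of 75 and 193 (total 268, as the 266 denominator df in Section 14 imply) changes the multiplier to 2.228 and the half-widths to 0.31 to 0.69.
- Without Table 14.2: with 52 and 146 and rho of .5, .7, .8 or .9, the half-width is 0.63, 0.49, 0.40 or 0.28. Rho must exceed about .92 before it falls below 0.25.

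**The case against.** The strongest reply is that the fault is one loose clause. The sentence after it is correctly worded, and the following paragraph reports possible effects in the MCI group, so the section does not wholly close the question. That is true and limits the point to the clause and the missing intervals. It does not rescue the clause, because the next sentence is presented as following from it.

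Supplementary Table B may hold the three-way estimates and their standard errors. It cannot be said that they were never reported, only that the main text and Table 14.3 give no intervals.

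The 0.25 benchmark was set in Sections 6.3.4 and 9.5 as an interim trigger for piano versus control on an individual cognitive measure. It is not a margin for a difference between strata on a composite, and it serves here only as a yardstick.

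It may also be said that Aim 2 was planned with .95 power. Planned power does not turn a non-significant result into evidence of no difference, and what matters now is the precision reached with 52 and 146.

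A reader might infer that sizeable benefit and harm in MCI are both left open. The documents do not support that. A difference between strata is not harm: for cognition, the MCI-only effect by the same method is 0.08 ± 0.32 (1.96 x 0.084 x √(198/52)), or -0.24 to 0.40. Nor do all intervals pass 0.25 on both sides. On the printed values, cognition passes it only towards more benefit with MCI, and verbal fluency and CAP clearly pass it only towards less.

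**Conclusion.** The clause is wrong as written: the analysis did not detect moderation by MCI status, and it does not show that there is none. Approximate 95% half-widths for the difference in effect run from 0.32 SD (CAP) to 0.70 SD (Timed IADL), with 0.37 for cognition. For each composite, a difference larger than 0.25 remains possible in at least one direction.

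The intervals are derived here and are not printed in the documents. They rest on SD-10 scaling, equal arms within each stratum and a common SD of change. The half-widths are firmer than the limits, because several subgroup d values in Table 14.3 look inconsistent.

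A reader might go further and infer that piano training does work differently in MCI, or that the plan itself must be amended. Neither follows. Every derived interval includes zero. Section 9.6 asked for effect sizes by MCI status and Table 14.3 supplies them. Data collection ended in April 2021, so a new commitment in the plan would be retrospective.

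**What to change.** - In Section 14, replace the clause with: *moderation by MCI status was not detected, but the estimates are too imprecise to exclude differences of about 0.3 to 0.7 SD*, using the fitted models' own limits in place of the approximate range.
- Give each three-way estimate with its 95% interval in the main text, taken from Supplementary Table B if it already holds them.
- Check the subgroup d values in Table 14.3, starting with the non-MCI cognitive composite of -0.10 and the Timed IADL and TEA composites. Then add a 95% interval to every d.
- Leave Section 9.6 as it is.

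The models are already fitted, so the cost is a revision of text and tables and a weaker claim for Aim 2.
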